3.1.1 Pre-Trial Activities and Screening Phase

The Remote Training Strategy was developed during Phase 1 of this 5-year project using an iterative process (*Rapid Prototyping*) to develop the appropriateness, feasibility, acceptability and preliminary efficacy of the online training platform.

School Selection: The National Center for Education Statistics (NCES) subdivides rural and town school areas by their proximity to an urbanized area into fringe, distant, or remote locations.⁴⁷ Participant schools will be located in any of these three rural locations or town, remote area and/or the school will serve rural communities. We will invite 24 schools representing the 2 geographic locations (urban/rural) to participate in the pilot efficacy study. After receiving school approval to participate schools will be stratified based on the geographic location and a computer-generated block randomization list will be prepared to randomize the 24 schools in a 1:1:1 ratio to either RV, RV+ or CC (8 schools/arm) stratified by geographic locations (urban/rural). The block randomization with varying will ensure ensure equal number of schools in each arm and eliminate the predictability of schools' assignment.

Behavioral Health Staff Screening: Recruitment will begin with assistance from the school principal who may nominate school behavioral health staff to participate in the study. Additionally, the research staff will reach out to school behavioral health staff concurrently with the school principal. The research staff will speak with school staff by phone or via WebEx to clearly explain study procedures, as well as potential risks and benefits. BHS will be clearly informed of the voluntary nature of their participation and will receive ample opportunities to ask questions. A copy of the consent form will be provided to the BHS, and consent will be obtained electronically via REDCap.

Student Screening: Recruitment of child participants will begin with research staff assisting school behavioral health staff who will examine teacher nomination data for students in specific grades and classes in order to identify students for Tier 2 interventions. We will train BHS remotely on providing a brief in-service training to teachers tasked with nominating students on recognizing warning signs of excessive anxiety, depression, and disruptive behavior problems in children, and completing the screening measures. Following the remote training, BHS will ask teachers from specific grades or classes to nominate students. **First**, teachers will be asked to rank order students and then select the top three students with externalizing problems and the top three students with internalizing problems. **Second**, parents and teachers will complete the SDQ (paper or electronically) on these identified students. **Third**, parents and teachers will give the SDQ forms to the BHS member (when applicable). **Fourth**, BHS will scan the SDQ to CHOP staff to score. **Fifth**, students who score above the specified cut-off on the externalizing or internalizing dimension will be selected for the next step, which will require BHS to contact the parents and request that they complete the SCARED or to ask a teacher of the student to complete the SAEBRS. **Sixth**, children who score at least 25 or there is an elevated subscale for the SCARED or if the student score on the Social Behavioral subscale of the SAEBRS is 12 or less, they will be considered for participation in one of the groups or in CI/CO. **The research aspect of the project will begin at this point.** Children who meet inclusion criteria will be invited to participate in the study. Research staff will ask parents to provide consent for their child to participate in the intervention. The children will also be asked to provide assent to participate in the intervention. Informed consent (parent) and assent (child) will be obtained by research staff prior to enrollment. Participating BHS will facilitate consent meetings with eligible children and their parents. A research staff member will join these meetings by phone or via a videoconference.

3.1.2 Phase 1: Training of Behavioral Health Staff

All initial trainings will be lead by research staff and will be conducted remotely via Webex. These initial trainings will be recorded and made available to all participants to reference for the duration of their participation in the study.

Initial Red Flags and Screening Training: Research staff will train school staff from all conditions remotely on identifying “red flags” that a student is struggling with anxiety, anger, or other mood disorders and how this information can help Tier 2 Team members and teachers make informed referrals for the interventions. Study participants should use this information to hold a brief professional development with school staff to help guide their referrals. Additionally, participants will be taught about how the referral and screening

process operates, including who is responsible for each aspect of the process, how the screening measures are scored and what those scores mean. We will train BHS using strategies that have been proven effective, including the teaching of the theoretical approach used in the intervention, active demonstration and practice of skills, and coaching. ^{56,57}

Initial Evidence-Based Programs Training: Research staff will train school staff from all conditions remotely on the three EBPs. The three EBPs that schools staff will be trained on are Coping Power Program (CPP) ⁵⁸ for externalizing behavior disorders, CBT for Anxiety Treatment in Schools (CATS) ⁵⁹ for anxiety disorders, and Check-in/Check-out (CI/CO) ⁶⁰ for externalizing and internalizing ⁶¹ disorders. Three separate trainings will be held to introduce participants to the interventions and provide an overview and understanding of each EBP.

Video Training Modules: We will offer protected access to asynchronous training materials to BHS in the Remote Video and Remote video plus coaching conditions. These trainings will include “modules” that are comprised of didactic content, audio and visual examples, as well as treatment materials and resources, all of which can be viewed at the trainee’s individual pace and convenience. Participants will have access to the training modules via CHOP OPEN and they will be able to login using a unique username and password.

3.2 Study Duration, Enrollment and Number of Sites

Behavioral Health Staff: BHS will be asked to commit to participate in the study for one school year. The school the BHS works at will be randomly selected as a participating school for either years 1,2, or 3 of the study. BHS will be free to implement the EBPs outside the research project after their participation in the study has concluded.

Students: Students who are eligible, based on the SDQ, SCARED, and SAEBRS, and for whom consent/assent is obtained, will participate in the study for the time it takes them to receive one of the interventions. Participation includes receiving interventions consisting of CI/CO, CPP, or CATS. The interventions will consist of one 40-minute/class period intervention session conducted at school or two brief daily check-ins also conducted during the school day. Post-treatment data will be collected by a parent/caregiver and teacher using the BASC-3 and Engagement versus Disaffection with Learning Teacher Report (EvsD-Teacher). Students will be asked to complete the Behavior and Feelings Survey.

Administrators: School principals and/or administrators will be asked to complete a qualitative interview about their experience with the project.. The interview will occur at the end of the academic year and their participation will last the time it takes to complete the interview

3.2.1 Total Number of Study Sites/Total Number of Subjects Projected

We will conduct the pilot trial in 24 schools (8 in Control Condition, 8 in Remote Video, and 8 in Remote Video plus Coaching. We anticipate enrolling 24 administrators (1 per school), 72 behavioral health staff (3 from each school; 24 in CC, 24 in RV, 24 in RV+) and 312 students (104 in CC, 104 in RV, 104 in RV+). We expect that each school will have one staff member with prior mental health training (e.g., school counselor). This staff member will be expected to implement one of the group-EBPs. The two other staff will be tasked

with implementing CICO, as this intervention can be implemented by school staff without prior mental health training.^{62,63} We estimate that each school staff will conduct one CPP or CATS group with 5-6 students of similar developmental level (e.g., a group of 4th & 5th graders; 144 students total), and that each school staff in CICO will implement the intervention with 6 individual students of any school grade (144 students total).

3.3 Study Population

3.3.1 Inclusion Criteria

Administrator: Any school principal or assistant principal from participating schools implementing PBIS.

Behavioral Health Staff: Any counselor, social worker, or teacher from participating schools implementing PBIS who work with students in grades 4-8.

Students: Inclusion of students to receive a Tier 2 intervention is as follows:

- attending one of the participating schools
- being in grades 4-8
- identified by the Tier 2 team as not responding to Tier 1 intervention, thus needing Tier 2 support
- scoring ≥ 1 SD above the mean on the Emotional Symptoms or Conduct Problems scales of the Strength and Difficulties Questionnaire (SDQ)⁵⁴ completed by a parent or a teacher

The cut-off score level for the SDQ is appropriate for identifying students at risk for a behavioral/mental health disorder^{54,55}. We limit participation to students in grades 4-8 because the group EBPs are appropriate for this age group.

3.3.2 Exclusion Criteria

Administrator: School staff who are not principals or assistant principals.

Behavioral Health Staff: School staff who are not part of the PBIS team and who do not work with students in grades 4-8.

Students: Students who do not meet screening or group participation criteria will not be included in the study. Students with a history of intellectual disability or serious developmental delays according to school records will not be included because they would be unlikely to benefit from the interventions used in the study. Students with a history of psychotic or autistic spectrum disorders as reported by parents will not be included.

Subjects that do not meet all the enrollment criteria may not be enrolled. Any violations of these criteria must be reported in accordance with IRB Policies and Procedures.

4 STUDY PROCEDURES

4.1 Screening and Consent Procedures

Please refer to Section 3.1.1 for detailed description of Screening and Consent Procedures.

Teachers will assist with screening procedures by completing screening measures for potentially eligible students in their class. Teachers are not considered study participants.

4.2 Phase 1: Training of Behavioral Health Staff

4.2.1 Initial Synchronous Trainings

Research consultants will conduct a synchronous (live) training workshop at the beginning of each year via a video-conferencing platform (Webex) for behavioral health staff. BHS will be instructed on the use of data to identify and assign students at risk for behavioral and emotional disorders into Tier 2. The BHS will also be taught a competency framework for mental health and PBIS^{77,78} strategies for enhancing school personnel knowledge of mental health “warning signs” among students, and how to access the online materials. The training related to “warning signs” will be conducted in order to help BHS identify students who could benefit from the interventions.

BHS will be instructed to use training manuals and will be trained on the use of a mental health screening instrument (SDQ)⁵⁴ and a multi-axial parent rating scale (Behavioral Assessment System for Children, Third Edition (BASC-3))⁶⁸ and other instruments used in the study. BHS will be introduced to a competency model for CBT⁷⁹. They will also learn about how to deal with implementation barriers (e.g., scheduling sessions, conducting exposure tasks)⁸⁰. Training content and procedures will be based on adult learning characteristics (e.g., propensity to learn from experience, capacity to reflect on performance and apply knowledge, and selfmotivation)^{81,82}.

4.2.2 Guided Video for Remote Video and Remote Video plus Coaching

Following the initial training workshop and after BHS have identified students for interventions, BHS in the RV and RV+ conditions will be given access to the training videos. The videos will be made available through CHOP OPEN that has the ability to measure how many times each video has been accessed by the BHS and for how long. Each participant will be given access to the videos that correspond to the interventions that they plan to use. All Tier 2 implementers in RV and RV+ will be given access to videos that address general topics (e.g., how to use data to identify students for participation; dealing with implementation barriers).

4.3 Phase 2: Implementation of EBPs

We expect that each school will have one staff member with prior mental health training (e.g., school counselor). This person will be expected to implement one of the group-EBPs. The two other staff members will be tasked with implementing CI/CO, as this intervention can be implemented by school staff without prior mental health training.^{63,68} We estimate that the staff member with mental health training will conduct one CPP or CATS group with 5-6 students of similar developmental level (e.g., a group of 4th & 5th graders; 144 students

total), and the other implementers will lead CI/CO and will implement the intervention with 6 individual students of any school grade (144 students total). Following the initial live training, BHS will be instructed to conduct targeted screenings with the grade group they would like to select for participation in the study.

Research consultants will provide technical assistance to support behavioral health staff. The three EBPs that schools will use for Tier 2 are the Coping Power Program (CPP)⁵⁸ for externalizing behavior disorders, CBT for Anxiety Treatment in Schools (CATS)⁵⁹ for anxiety disorders, and Check-in/Check-out (CI/CO)⁶⁰ for externalizing⁶¹ disorders. CPP and CATS will be implemented in group format with students of similar developmental level (e.g., 4th & 5th or 7th & 8th grade together) during the lunch or free period. BHS could also use CI/CO for individual students who do not meet inclusion criteria for CPP or CATS. Each school will be instructed to select CI/CO and one of the two CBT protocols for use.

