This study is designed to test the effectiveness of initial training compared to remote video training and remote video training plus coaching to train BHS to implement EBPs. Each school will be randomly assigned to receive one of three training supports: (a) Initial training (CC) (b) Initial training, plus video (RV) or (c) Initial training plus video, plus remote coaching (RV+). BHS in the RV+ condition will receive consultation from a CHOP consultant regarding implementation of EBPs, whereas BHS in the RV condition will be given access to the asynchronous training video modules. Participants in all three conditions will receive treatment manuals for the interventions they have chosen. The EBPs to be implemented by the BHS include: Coping Power Program (CPP), CBT for Anxiety Treatment in Schools (CATS), and Check-in/Check-out (CI/CO). All BHS will conduct one CPP or CATS group with 5 students of similar developmental level (e.g., a group of 4th &

5th graders), and that each school staff in CI/CO will implement the intervention with 4 separate individual students of any eligible school grade.

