6.4 Sample Size and Power

The proposed pilot study aims to collect data and estimate effect sizes measuring the effect of RV and RV+ when compared to the CC. Although, this pilot study is not powered to test for specific hypotheses regarding effect sizes, the sample size estimates were based on data obtained from our recently completely NIH funded study, ^{15,77} we estimated that a total of 72 BHS (24 per arm) and 312 students will participate in this study. With 24 BHS per arm, a two-sided 95% confidence interval in mean differences in content fidelity (CF) and process fidelity (PF between) RV or RV+ vs. CC will be produced. The minimum distance from the mean difference to the limits (margins of error) will equal to 9.3 (CF) and 0.35 (PF) with the estimated pooled standard deviations equal to 16 and 0.6 respectively. It is anticipated that 104 students per arm will be recruited (total = 312). Assuming a uniform attrition rate of 15%, a total of 268 evaluable students will be included in the final statistical analysis. With 89 students in each of the three study arms, a two-sided 95% confidence interval for mean differences in pre/post changes in student mental health symptoms and academic engagement between the two arms ((RV or RV+) vs. CC) will equal to 2.4 with estimated

pooled standard deviation equal to 8. Sample size justification was reported using PASS 13 software.⁷⁸

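### Section 3.2.1 projects 312 students, but its own subtotals sum to 288 and its per-staff CI/CO load gives 408 to 432; Section 4.3 repeats the subtotals

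*Combined protocol and SAP*

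**What the plan says.** **Schools and staff.** Section 3.2.1: "We will conduct the pilot trial in 24 schools", with "72 behavioral health staff (3 from each school; 24 in CC, 24 in RV, 24 in RV"+ arms. Section 4.3 divides the three staff in each school: "We expect that each school will have one staff member with prior mental health training (e.g., school counselor", who runs a group, and "The two other staff members will be tasked with implementing CI/CO". Section 3.2.1 describes the same split.

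**Planned students.** Section 3.2.1 projects "312 students (104 in CC, 104 in RV, 104 in RV"+. The same 312 appears in the abstract, Section 6.4 and Section 8.1.1. The abstract and 8.1.1 add that this is 13 per school.

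**Students per staff member, abstract.** Groups have 5 students, and "each school staff in CI/CO will implement the intervention with 4 separate individual students of any eligible school grade".

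**Students per staff member, Section 3.2.1.** Groups have 5 to 6 students, with a stated total of 144. Each CI/CO staff member takes 6 students, also with a stated total of 144.

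**Students per staff member, Section 4.3.** The group size and group total are the same as in 3.2.1, and then "the other implementers will lead CI/CO and will implement the intervention with 6 individual students of any school grade (144 students total".

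**Precision.** Section 6.4 assumes 15% attrition and says that "a total of 268 evaluable students will be included in the final statistical analysis". It uses 89 per arm and an SD of 8 to state a 95% confidence interval margin of 2.4.

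**The concern.** Section 3.2.1 gives a total and two subtotals in one paragraph, and they disagree. Its per-person CI/CO load also disagrees with its own CI/CO subtotal by a factor of two. Section 4.3, which tells schools how to run the interventions, carries the same subtotals. The abstract uses different loads for both the groups and CI/CO.

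A site or study coordinator could therefore take three different enrolment targets from one protocol. The number of students per school is at stake, and the school is the unit of randomization. So is the balance between CI/CO and group students, whose implementers' fidelity is measured with different instruments (Section 5.3).

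**Working it through.** **Inputs.** 24 schools. One group leader per school gives 24. Two CI/CO staff per school gives 48. Together these are the 72 staff in 3.2.1.

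**Step 1. Reproduce the planned total.** Abstract loads with the 3.2.1/4.3 staffing:
- group: 24 x 5 = 120
- CI/CO: 48 x 4 = 192
- total: 120 + 192 = 312, or 5 + 4 + 4 = 13 per school and 104 per arm. This matches the plan exactly.

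**Step 2. Reproduce the planned margin.** Half-width = t x SD x sqrt(2/n). With n = 89 and SD = 8 it is 2.37 (2.35 with z = 1.96). Section 6.4 states 2.4, so this also reproduces.

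**Step 3. Section 3.2.1.**
- Sum of its stated subtotals: 144 + 144 = 288, or 288 / 24 = 12 per school.
- Group subtotal from its group size: 24 x 5 = 120 to 24 x 6 = 144. The stated 144 holds only if every group has 6.
- CI/CO subtotal from its per-person load: 48 x 6 = 288, twice the stated 144.
- Total from its own loads: 120 + 288 = 408 to 144 + 288 = 432, or 17 to 18 per school.

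**Step 4. Section 4.3 read alone.** If the 6 are shared by the two CI/CO implementers, 24 x 6 = 144, as stated. Adding groups of 5 to 6 gives 120 + 144 = 264 to 144 + 144 = 288, or 11 to 12 per school.

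**Step 5. Side by side.** Evaluable per arm is (total / 3) x 0.85. The margin is 1.96 x 8 x sqrt(2/n), with students treated as independent.

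| Reading | Total | Per school | CI/CO share | Evaluable per arm | Margin |
|---|---|---|---|---|---|
| 4.3 alone, groups of 5 | 264 | 11 | 144/264 = 55% | 74.8 | 2.56 |
| Stated subtotals (also 4.3 with groups of 6) | 288 | 12 | 144/288 = 50% | 81.6 | 2.45 |
| Abstract loads | 312 | 13 | 192/312 = 62% | 88.4 | 2.36 |
| 3.2.1 loads, groups of 5 | 408 | 17 | 288/408 = 71% | 115.6 | 2.06 |
| 3.2.1 loads, groups of 6 | 432 | 18 | 288/432 = 67% | 122.4 | 2.00 |

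Only the abstract loads give 312.

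**Step 6. Evaluable total.** 312 x 0.85 = 265.2. Per arm, 104 x 0.85 = 88.4, which rounds up to 89, and 3 x 89 = 267. The stated 268 matches neither. With t, the margin is 2.38 at 88 per arm and 2.37 at 89, so 2.4 either way.

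**The case against.** The strongest reply is that the planned sample size is sound. The 312 is stated in four places, follows from the abstract's loads, and leads to the 2.4 in Section 6.4. A reader might infer from the conflict that 312 itself has no basis. The documents do not support that, and this part of the reply stands in full.

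A second reply concerns Section 4.3. A reader might infer that a school following it would enrol up to 18 students. The sentence does not say that each implementer takes 6, and its total of 144 fits 6 per school. The 17 to 18 comes from Section 3.2.1, where the load is per person. This reply also stands, but the shared reading still reaches only 264 to 288.

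A third reply is that the word *each* is used loosely. Taken literally, the abstract and 3.2.1 have every staff member run a group, which clearly is not meant, so the CI/CO *each* might be loose too. That weakens 408 to 432 as a statement of intent. It does not rescue 3.2.1, whose 144 + 144 differs from its 312 however *each* is read. The one-plus-two staffing used in Step 1 is likewise taken from 3.2.1 and 4.3, because the abstract does not state it.

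Finally, these are estimates in a pilot that is not powered for hypotheses, and the margin moves little. That is fair, and it limits the severity. It does not make contradictory enrolment figures acceptable.

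**Conclusion.** The inconsistency is real and lies in the loads and subtotals of Sections 3.2.1 and 4.3. Section 3.2.1 contradicts itself twice: 288 against 312 in total, and 288 against 144 for CI/CO. Section 4.3 repeats the subtotals and does not reach 312 on any reading. The 312 total and the 2.4 margin agree with each other.

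The range is 264 to 432 students against 312, and 11 to 18 per school against 13. CI/CO would make up 50% to 71% of students, against 62% under the abstract's loads. The margin runs from about 2.0 to 2.5 for totals of 432 down to 288, and is 2.6 at 264. These margins assume an SD of 8, 15% attrition and independent students. The documents give no intraclass correlation, so the effect of cluster size on a clustered analysis is not quantified here.

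A reader might also treat 268 as a substantive error. It is a rounding-level discrepancy that leaves the margin unchanged. The documents do not settle which recipe was intended.

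**What to change.** Reconcile the abstract, 3.2.1, 4.3, 6.4 and 8.1.1 to one per-school recipe. It should give the number of group leaders and CI/CO staff, students per group, students per CI/CO staff member (saying that it is per person), and totals that follow from these.

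- If 312 is kept, 5 + 4 + 4 = 13 per school reproduces it, with 120 group and 192 CI/CO students. Both 144 figures in 3.2.1 and in 4.3, and the loads printed beside them, must then be replaced. This is a wording correction with no added enrolment.
- If another recipe is intended, the 312, the 104 per arm, the 13 per school and the student precision figures in 6.4 must be restated. At 408 to 432 that means 96 to 120 more students than now projected; at 264 to 288 it means 24 to 48 fewer.

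In the same edit, make the evaluable total agree with the per-arm number. With 89 per arm it is 267. Writing 265 with 88 per arm would not sum either, since 3 x 88 = 264. The 2.4 margin need not change for this.
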